7.2.2.6.5 Coagulation

International normalized ratio (INR) and prothrombin time (PT) or Quick Test will be measured at screening only.

7.2.2.7 Cardiac assessments

7.2.2.7.1 Electrocardiogram (ECG)

A standard 12 lead ECG will be performed as described in [Table 7-5](#).

- At the screening visit in triplicate for all patients and
- At other defined time points as triplicate ECGs for all patients [REDACTED] (Table 7-5).

Baseline is defined as the pre-dose assessment on Cycle 1 Day 1 before study drug administration.

All ECGs recorded for each time point will be transmitted electronically to a central laboratory and will be centrally reviewed by an independent reviewer in a blinded fashion in regards to time, and day (i.e., Cycle 1 Day 1, Cycle 2 Day 1) identifiers. Any original ECG not transmitted electronically to the central laboratory should be forwarded for central review. Review of all ECGs from a particular patient should be performed by a single reader. The ECG lead for interval duration measurements should be pre-specified. Baseline and all subsequent ECGs should be based on the same lead.

Detailed instructions regarding the ECG collection will be provided to the investigators in a separate manual prior to the start of the study. [REDACTED]

[REDACTED] The triplicate ECGs should be taken approximately 2-4 minutes apart.

An ECG may be repeated at the discretion of the investigator at any time during the study and as clinically indicated. Each ECG tracing should be labeled with the study number, patient initials (where regulations permit), patient number, date, and kept in the source documents at the study site.

[figure not shown]
[figure not shown]
[figure not shown]
[figure not shown]
[figure not shown]

[figure not shown]
Table 7-5 ECG collection plan for patients [REDACTED] (triplicate ECGs)

Cycle	Day	Time	ECG Type
Screening	-28 to -1	Anytime	12 Lead
1	1	Predose	12 Lead
1	8	Predose	12 Lead
1	15	Predose	12 Lead
2	1	Predose	12 Lead
2	1	any time between 4 to 10 hr postdose	12 Lead
3	1	Predose	12 Lead
4	1	Predose	12 Lead
5	1	Predose	12 Lead
6	1	Predose	12 Lead
Subsequent cycles and EOT	1	Predose	12 Lead

Clinically significant abnormalities present when the patient signed informed consent should be reported on the Medical History eCRF page. Clinically significant findings must be discussed with Novartis prior to enrolling the patient in the study. New or worsened clinically significant findings occurring after informed consent must be recorded on the Adverse Events eCRF page.

[figure not shown]

[figure not shown]
[figure not shown]
7.2.4 CSF sampling in patients with leptomeningeal carcinomatosis at baseline

[figure not shown]
[figure not shown]
For patients presenting with a baseline leptomeningeal carcinomatosis (LC), diagnosis must be confirmed with documented malignant cells in the cerebrospinal fluid, or if suspected, supported by imaging findings on the Gadolinium-enhanced MRI of the brain or spine (in this latter case, the determination of the presence of malignant cells in CSF cytology is strongly recommended and a CSF sample for cytological evaluation should be taken within the 14 days before initiation of study drug at C1D1). Patients with known and documented positive cytology at screening do not need to be retested. Samples should be obtained from site of disease or initially positive cytology if possible.

During the study CSF will be collected at a frequency determined by local clinical practice unless medically contra-indicated and/or deemed to be an unacceptable burden to patient. The investigator may determine if more frequent evaluations are needed in case of suspected disease progression and/or in accordance with local clinical practice. If there are any signs or radiologic or clinical neurological progression, a CSF will be collected if feasible. Clinical progression may be determined based on results of cytological or neurological evaluations.

Before any CSF collection, the treating physician should rule out any medical condition that would prevent the safe conduct of a lumbar puncture, including but not limited to an increased intracranial pressure, a thrombocytopenia or a bleeding diathesis, an active infection.

7.2.6 Resource utilization

Direct collection of health care resource utilization (HCRU) data related to the treatment of brain metastases will be collected (such as hospitalization, inpatient and outpatient treatment, radiotherapy and radiosurgery).

7.2.7 Patient reported outcomes

Not applicable.

8 Safety monitoring and reporting

8.1 Adverse events

[figure not shown]
8.1.1 Definitions and reporting

An adverse event is defined as the appearance of (or worsening of any pre-existing) undesirable sign(s), symptom(s), or medical condition(s) that occur after patient's signed informed consent has been obtained.

For patients whose ALK status is unknown and who sign the molecular pre-screening ICF, AEs which occur after signature of this consent will only be captured if they meet the definition of serious as outlined in [Section 8.2](#) and are reported to be causally related to study procedures (e.g. an invasive procedure such as biopsy). Once the main study ICF is signed, all AEs per the descriptions below will be captured in the Adverse Event eCRF. Abnormal laboratory values or test results occurring after informed consent constitute adverse events only if they induce clinical signs or symptoms, are considered clinically significant, require therapy (e.g., hematologic abnormality that requires transfusion or hematological stem cell support), or require changes in study medication(s).

Adverse events that begin or worsen after informed consent should be recorded in the Adverse Events eCRF. Conditions that were already present at the time of informed consent should be recorded in the Medical History page of the patient's eCRF. Adverse event monitoring should be continued for at least 30 days (or 5 half-lives, whichever is longer) following the last dose of study treatment. Adverse events (including lab abnormalities that constitute AEs) should be described using a diagnosis whenever possible, rather than individual underlying signs and symptoms. When a clear diagnosis cannot be identified, each sign or symptom should be reported as a separate Adverse Event.

Adverse events will be assessed according to the Common Terminology Criteria for Adverse Events (CTCAE) version 4.03 (dated 14 June 2010). If CTCAE grading does not exist for an adverse event, the severity of mild, moderate, severe, and life-threatening, corresponding to Grades 1 - 4, will be used. CTCAE Grade 5 (death) will not be used in this study but is collected as seriousness criteria; rather, information about deaths will be collected through a Death eCRF.

Abnormal laboratory values or test results occurring after signing the ICF constitute adverse events only if they induce clinical signs and symptoms, or require therapy, (e.g., any hematologic abnormality that requires transfusion of hematological stem cell support) or changes in medication(s) are considered clinically significant and should be recorded on the Adverse Event eCRF under signs, symptoms or diagnosis associated with them. In addition, isolated abnormal laboratory values that are considered clinically significant (e.g. cause study discontinuation or constitute in and of itself a Serious Adverse Event) should be recorded on the Adverse Events eCRF.

The occurrence of adverse events should be sought by non-directive questioning of the patient (subject) during the screening process after signing informed consent and at each visit during the study. Adverse events also may be detected when they are volunteered by the patient (subject) during the screening process or between visits, or through physical examination, laboratory test, or other assessments. As far as possible, each adverse event should be evaluated to determine:

- The severity grade (CTCAE Grade 1-4)
- Its duration (Start and end dates)
- Its relationship to the study treatment (Reasonable possibility that AE is related: No, Yes)
- Action taken with respect to study or investigational treatment (none, dose adjusted, temporarily interrupted, permanently discontinued, unknown, not applicable)
- Whether medication or therapy was given (no concomitant medication/non-drug therapy, concomitant medication/non-drug therapy)
- Outcome (not recovered/not resolved, recovered/resolved, recovering/resolving, recovered/resolved with sequelae, fatal, unknown)
- Whether it is serious, where a serious adverse event (SAE) is defined as in [Section 8.2.1](#) and which seriousness criteria have been met

All adverse events should be treated appropriately. If a concomitant medication or non-drug therapy is given, this action should be recorded on the Adverse Event CRF.

Once an adverse event is detected, it should be followed until its resolution or until it is judged to be permanent, and assessment should be made at each visit (or more frequently, if necessary) of any changes in severity, the suspected relationship to the study treatment, the interventions required to treat it, and the outcome.

Progression of malignancy (including fatal outcomes), if documented by use of appropriate method (for example, as per RECIST criteria for solid tumors or as per Cheson's guidelines for hematological malignancies), should not be reported as a serious adverse event.

Adverse events separate from the progression of malignancy (example, deep vein thrombosis at the time of progression or hemoptysis concurrent with finding of disease progression) will be reported as per usual guidelines used for such events with proper attribution regarding relatedness to the drug.

8.1.2 Laboratory test abnormalities

8.1.2.1 Definitions and reporting

Laboratory abnormalities that constitute an Adverse event in their own right (are considered clinically significant, induce clinical signs or symptoms, require concomitant therapy or require changes in study treatment), should be recorded on the Adverse Events CRF. Whenever possible, a diagnosis, rather than a symptom should be provided (e.g. anemia instead of low hemoglobin). Laboratory abnormalities that meet the criteria for Adverse Events should be followed until they have returned to normal or an adequate explanation of the abnormality is found. When an abnormal laboratory or test result corresponds to a sign/symptom of an already reported adverse event, it is not necessary to separately record the lab/test result as an additional event.

Laboratory abnormalities, that do not meet the definition of an adverse event, should not be reported as adverse events. A Grade 3 or 4 event (severe) as per CTCAE does not automatically indicate a SAE unless it meets the definition of serious as defined below and/or as per investigator's discretion. A dose hold or medication for the lab abnormality may be required by the protocol in which case the lab abnormality would still, by definition, be an adverse event and must be reported as such.

8.2 Serious adverse events

8.2.1 Definitions

Serious adverse event (SAE) is defined as one of the following:

- Is fatal or life-threatening
- Results in persistent or significant disability/incapacity
- Constitutes a congenital anomaly/birth defect
- Is medically significant, i.e., defined as an event that jeopardizes the patient or may require medical or surgical intervention to prevent one of the outcomes listed above
- Requires inpatient hospitalization or prolongation of existing hospitalization,
- Note that hospitalizations for the following reasons should not be reported as serious adverse events:
 - Routine treatment or monitoring of the studied indication, not associated with any deterioration in condition

- Elective or pre-planned treatment for a pre-existing condition that is unrelated to the indication under study and has not worsened since signing the informed consent
- Social reasons and respite care in the absence of any deterioration in the patient's general condition
- Note that treatment on an emergency outpatient basis that does not result in hospital admission and involves an event not fulfilling any of the definitions of a SAE given above is not a serious adverse event

8.2.2 Reporting

For patients with unknown ALK mutational status and who sign the molecular pre-screening ICF, SAE collection will start upon signing the molecular pre-screening ICF. SAEs will only be reported if the event is suspected to be causally related to a study procedure as assessed by the investigator (e.g., an invasive procedure such as biopsy). SAEs will be followed until resolution or until clinically relevant improvement or stabilization. If the main ICF is not signed (molecular screen failure), SAE collection ends 30 days after the last study related procedures.

For patients with known ALK mutational status who sign the main study ICF, SAE collection starts at time of main study informed consent whether the patient is a screen failure or not.

To ensure patient safety, every SAE, regardless of suspected causality, occurring after the patient has provided informed consent and until at least 30 days after the patient has stopped study treatment must be reported to Novartis within 24 hours of learning of its occurrence.

Any additional information for the SAE including complications, progression of the initial SAE, and recurrent episodes must be reported as follow-up to the original episode within 24 hours of the investigator receiving the follow-up information. An SAE occurring at a different time interval or otherwise considered completely unrelated to a previously reported one should be reported separately as a new event.

Any SAEs experienced after this 30 days period should only be reported to Novartis if the investigator suspects a causal relationship to the study treatment.

Information about all SAEs is collected and recorded on the Serious Adverse Event Report Form; all applicable sections of the form must be completed in order to provide a clinically thorough report. The investigator must assess and record the relationship of each SAE to each specific study treatment (if there is more than one study treatment), complete the SAE Report Form in English and submit the completed form within 24 hours to Novartis. Detailed instructions regarding the submission process and requirements for signatures are to be found in the investigator folder provided to each site.

Follow-up information is submitted in the same way as the original SAE Report. Each re-occurrence, complication, or progression of the original event should be reported as a follow-up to that event regardless of when it occurs. The follow-up information should describe whether the event has resolved or continues, if and how it was treated, and whether the patient continued or withdrew from study participation.

If the SAE is not previously documented in the Investigator's Brochure or Package Insert (new occurrence) and is thought to be related to the Novartis study treatment, an oncology

Novartis Chief Medical Office and Patient Safety (CMO&PS) department associate may urgently require further information from the investigator for Health Authority reporting. Novartis may need to issue an Investigator Notification (IN), to inform all investigators involved in any study with the same drug that this SAE has been reported. Suspected Unexpected Serious Adverse Reactions (SUSARs) will be collected and reported to the competent authorities and relevant ethics committees in accordance with Directive 2001/20/EC or as per national regulatory requirements in participating countries.

8.3 Emergency unblinding of treatment assignment

Not applicable. This is an open-label study.

8.4 Pregnancies

To ensure patient safety, each pregnancy occurring while the patient is on study treatment must be reported to Novartis immediately (within 24 hours) of learning of its occurrence. Patients who become pregnant during the trial must be withdrawn. The pregnancy will be followed up from the estimated date of delivery plus 3 months to determine outcome, including spontaneous or voluntary termination, details of the birth, and the presence or absence of any birth defects, congenital abnormalities, or maternal and/or newborn complications.

Pregnancy should be recorded on a Clinical Trial Pregnancy Form and reported by the investigator to the oncology Novartis DS&E. Pregnancy follow-up should be recorded on the same form and should include an assessment of the possible relationship to the investigational treatment of any pregnancy outcome. Any SAE experienced during pregnancy must be reported on the SAE Report Form.

Pregnancy outcomes must be collected for the female partners of any males who took study treatment. A pregnancy outcome informed consent will be provided by Novartis. Consent to report information regarding these pregnancy outcomes should be obtained from the mother.

Women of childbearing potential should be advised to use highly effective contraception methods while they are receiving study treatment and up to 3 months after treatment has been stopped.

If a pregnancy occurs while on study treatment, the newborn will be followed for at least 3 months.

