 - 15a. Women of child-bearing potential, defined as all women physiologically capable of becoming pregnant, **unless** they are using highly effective methods of contraception during dosing and for 3 months after stopping medication. Highly effective contraception methods include:
 - Total abstinence (when this is in line with the preferred and usual lifestyle of the subject. Periodic abstinence (e.g., calendar, ovulation, symptothermal, post-ovulation methods) and withdrawal are not acceptable methods of contraception)
 - Female sterilization (have had surgical bilateral oophorectomy with or without hysterectomy), total hysterectomy, or tubal ligation at least six weeks before taking study treatment. In case of oophorectomy alone, only when the reproductive status of the woman has been confirmed by follow up hormone level assessment
 - Male sterilization (at least 6 months prior to screening). The vasectomized male partner should be the sole partner for that subject
 - Use of oral, injected or implanted hormonal methods of contraception or placement of an intrauterine device (IUD) or intrauterine system (IUS), or other forms of hormonal contraception that have comparable efficacy (failure rate <1%), for example hormone vaginal ring or transdermal hormone contraception.

In case of use of oral contraception, women should have been stable on the same pill for a minimum of 3 months before taking study treatment.

16. Sexually active males unless they use a condom during intercourse while taking the drug and for 3 months after the last dose of ceritinib treatment. Male patients should not father a child for 3 months after the last dose of ceritinib treatment. A condom is required to be used also by vasectomized men in order to prevent delivery of the drug via seminal fluid.
17. Patient has other severe, acute, or chronic medical conditions including uncontrolled diabetes mellitus or psychiatric conditions or laboratory abnormalities that in the opinion of the investigator may increase the risk associated with study participation, or that may interfere with the interpretation of study results.
18. Patient has history of interstitial lung disease or interstitial pneumonitis, including clinically significant radiation pneumonitis (i.e., affecting activities of daily living or requiring therapeutic intervention).
19. Patient has a history of pancreatitis or a history of increased amylase or lipase that was due to pancreatic disease.

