7.2.2.6.4 Pregnancy and assessments of fertility

During screening, a serum pregnancy test will be completed (Day -28 to Day -1). On Cycle 1 Day 1 prior to dosing and at subsequent cycles and at EOT, urinary pregnancy test (dipstick) will be performed. The time windows granted for pregnancy testing are identical to the corresponding visit time windows for each visit. Refer to [Table 7-1](#). If local requirements dictate otherwise, local regulations should be followed.

Women who are determined not to be of child bearing potential before the study will only be tested at screening. When non-child bearing potential status is determined during the study, further pregnancy testing will not be continued. Women are considered post-menopausal if they have had 12 months of natural (spontaneous) amenorrhea with an appropriate clinical profile (e.g. age appropriate, history of vasomotor symptoms), and otherwise not of child bearing potential if they have had surgical bilateral oophorectomy (with or without hysterectomy) or tubal ligation at least six weeks ago. In the case of oophorectomy alone, only when the reproductive status of the woman has been confirmed by follow up hormone

level assessment is she considered not of child bearing potential (such testing is not covered as part of the study assessments). If local requirements dictate otherwise, local regulations should be followed.

The time windows granted for pregnancy testing are identical to the corresponding visit time windows for each visit. Refer to [Table 7-1](#).

If a positive pregnancy test is performed in between study visits, the patient must immediately notify the investigator.

Male patients must notify the investigator in case their partner is confirmed with positive pregnancy test results during the treatment period.

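### The protocol's pregnancy-reporting duty ends with study treatment, but its own contraception window runs 3 months longer, so a post-treatment pregnancy can go unreported

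*Protocol*

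**What the plan says.** The protocol sets a reproductive-risk window in three places. Exclusion 15a (section 5.3) bars women of child-bearing potential unless "they are using highly effective methods of contraception during dosing and for 3 months after stopping medication". Exclusion 16 requires condom use over the same period and adds: "Male patients should not father a child for 3 months after the last dose of ceritinib treatment". Section 8.4 repeats the period for women, who are to be advised to use contraception "while they are receiving study treatment and up to 3 months after treatment has been stopped".

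The collection rules are tied to treatment instead. In section 8.4, "each pregnancy occurring while the patient is on study treatment must be reported to Novartis immediately (within 24 hours) of learning of its occurrence". The newborn rule has the same condition: "If a pregnancy occurs while on study treatment, the newborn will be followed for at least 3 months". In section 7.2.2.6.4, "Male patients must notify the investigator in case their partner is confirmed with positive pregnancy test results during the treatment period". That section and Table 7-1 schedule pregnancy tests at screening, on Cycle 1 Day 1, at later cycles and at the end-of-treatment visit. None is scheduled after that.

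Section 8.4 also says: "The pregnancy will be followed up from the estimated date of delivery plus 3 months to determine outcome". The sentence goes on to name terminations among the outcomes to be determined.

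**The concern.** A protocol that asks patients to avoid conception for 3 months after the last dose treats those months as a period in which a pregnancy matters. One would expect the duty to report a pregnancy to cover the same months. Here, the 24-hour duty, newborn follow-up and male notification all stop with treatment.

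At stake is safety information. Section 11.3 has women told that the risk to a fetus is unknown. While it is unknown, each pregnancy inside the precautionary window is informative, and the sponsor would want to hear of it early enough to follow it. Efficacy is not involved.

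**Working it through.** No statistical figure in the plan needs reproducing. The check is a comparison of windows, with a little day arithmetic.

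**Side by side**

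| Rule | Where | Ends |
|---|---|---|
| Contraception, women | Exclusion 15a; section 8.4 | 3 months after treatment |
| Condom use and not fathering a child, men | Exclusion 16 | 3 months after last dose |
| 24-hour pregnancy report | Section 8.4 | End of study treatment |
| Newborn follow-up | Section 8.4 | Applies to pregnancies on study treatment |
| Men notify a partner's positive test | Section 7.2.2.6.4 | End of treatment period |
| Last scheduled pregnancy test | Section 7.2.2.6.4, Table 7-1 | End-of-treatment visit, within 7 days of last dose (section 4.1.2.3) |
| General adverse-event follow-up | Sections 7.1.6.1, 8.1.1 | 30 days after last dose, or 5 half-lives if longer |
| Later contacts | Sections 4.1.2.3, 7.1.6.3 | Continue, but ask only about survival and new anticancer therapy |
| Partner pregnancy outcomes | Section 8.4 | No time limit stated |

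**Arithmetic**, with the SAP's month of 30.4375 days (SAP section 4.3):

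- Length of the post-treatment window: 3 × 30.4375 = 91.3 days.
- Days of it covered by the 24-hour reporting sentence: 0, because that sentence stops at treatment.
- Days of it after the last scheduled test: at least 91.3 − 7 = 84.3.
- Days of it after general adverse-event follow-up: at most 91.3 − 30 = 61.3. This is an upper limit because the half-life is not given in the documents and section 8.1.1 may lengthen the period.

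The last two lines describe how a site might come to hear of a pregnancy. They do not measure the reporting duty, and only the second line does.

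**Two cases**

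1. *A woman conceives 6 weeks after her last dose.* She is inside the contraception window. She is past her last scheduled test, and the 24-hour sentence does not apply to her. Unless 5 half-lives exceed 6 weeks, general adverse-event follow-up has also ended. No contact asks about pregnancy.
2. *A man's partner tests positive 5 weeks after his last dose.* He is not told to notify the site, because section 7.2.2.6.4 stops at the treatment period. Section 8.4 nevertheless expects the partner's outcome to be collected. The collection duty is wider than the notification duty that would have to feed it.

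**The case against.** The documents contain several partial safety nets, and the case against rests on them.

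- *Partners.* Section 8.4 requires outcomes for female partners of any man who has taken the drug. This stands. A reader might infer that late pregnancies escape every reporting trigger, and for men that is wrong. What remains for men is the mismatch with section 7.2.2.6.4.
- *Untimed sentences for patients.* Section 8.4 says that pregnancy goes on a dedicated form and is reported, and that patients who become pregnant during the trial are withdrawn. Section 7.1.4 counts survival follow-up as being on the study. Section 14.2.31 lists pregnancy as a reason for ending post-treatment follow-up. These sentences could be read broadly. But the form sentence follows a duty expressly limited to treatment, and withdrawal or a disposition entry is not a safety report.
- *Positive tests between visits.* Section 7.2.2.6.4 tells the patient to inform the investigator of one. No end date is given, so this may bring the news to the site. It depends on the patient having a test, and it does not widen what the site must then send to the sponsor.
- *Serious adverse events.* A congenital anomaly is serious (section 8.2.1), and events suspected to be related stay reportable after 30 days (section 8.2.2). This stands, but it works only after the birth, if the site learns of it and suspects the drug.
- *Other instructions.* Local testing requirements may apply, and the consent form, pregnancy form and investigator folder cannot be seen here.

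The follow-up sentence could also be read as starting 3 months after the due date, so that losses and terminations fall outside it. Its own list of outcomes shows that this is not meant. It is a slip in one word.

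**Conclusion.** The mismatch is real, and it lies within the protocol. For female patients, no provision expressly extends pregnancy reporting into the 3 months after the last dose, so a pregnancy beginning then *can* go unreported as a pregnancy. For men, the notification duty is narrower than the collection duty it should serve.

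The size is modest. Contraception is already required through the window, so few events are to be expected. Sample size, ORR, DCR and all other efficacy analyses are untouched.

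Three stronger readings are tempting, and the documents do not support them:

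- That such pregnancies *will* be missed. The partial nets may catch some.
- That all enrolled patients pass through the window at risk. Some cannot conceive, some die on or soon after treatment, and some continue ceritinib elsewhere. The number at risk is not given.
- That a conception late in the window is a proven fetal exposure. That depends on the half-life, which is not given, and a contraception period may include a precautionary margin.

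The verdict assumes that study treatment and treatment period mean the time on ceritinib, and that no document outside the protocol and SAP widens the duty.

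**What to change.** Reconcile sections 5.3, 7.2.2.6.4 and 8.4, leaving the contraception rules as they are:

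1. In section 8.4, extend 24-hour reporting and outcome and newborn follow-up to pregnancies, in patients or female partners, that begin on treatment or within the protocol's existing 3 months after it.
2. In section 7.2.2.6.4, give the men's notification duty the same end point.
3. Add one question about pregnancy to the 30-day safety contact and to the first survival contact. If that contact falls 12 weeks after the last dose (12 × 7 = 84 days), about 91.3 − 84 = 7.3 days of the window come later, and a recent conception may not yet be recognised. The duty should therefore depend on when the pregnancy began, not on the date of the contact.
4. In the follow-up sentence of section 8.4, replace *from* with *until*.

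The cost is amendment wording and one question at contacts already planned. The downside is a slightly longer collection window, with some outcomes arriving after study close.
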